#### **5.2.1.1 Responder Analyses**

Survival techniques will be applied to data assessing time to increase in ADAS-cog of 7 points (based on meta-analysis published by Vellas, et al; 2007). For assurance that the results are not an artifact of the cut-point, analysis will be done for time to increases of each point from 1 to 20. Logrank and Wilcoxon tests will be done as descriptive analyses. Hazard ratios will be examined as descriptive analyses.

A forest plot will be produced to evaluate the sensitivity to the cut-point of the responder analysis.

#### **5.2.1.2 Other Descriptive Analysis**

Descriptive summaries will be produced of the observed values and change from Baseline in co-primary variables by treatment group at each individual time point and at endpoint (final on-treatment assessment for each subject).

For statistical analyses, 95% confidence intervals will be produced for the least-squares means (LSM) in each treatment group, as well as the LSM differences as compared to placebo plus SoC. For MMRM and ANCOVA, two-sided p-values will be displayed for the comparison against placebo plus SoC.

#### **5.2.1.3 Investigator Sites**

Because there are limited numbers of subjects per center, there is inadequate power to explore the impact of the center effect on study conclusions. Descriptive statistics by center or center-pool will be presented.

#### **5.2.1.4 Per Protocol Set**

If the PPS differs from the FAS by more than 15%, the analyses will be replicated on the PPS. If the PPS and the FAS do not differ by more than 15%, analysis may not be done on the PPS.

#### **5.2.1/5 Adjustments for multiplicity**

Multiplicity of the primary efficacy analyses is controlled by using a conditional sequence of hypotheses. The study will be considered to demonstrate statistical significance if the primary analysis has a resulting p-value less than 0.049 for both primary endpoints for both A-study and B-study. No other adjustment for multiplicity is required.

## 5.2.2 Statistical Methods for Secondary Variables

Secondary and exploratory endpoints that are measurement variables will use similar statistical methodology to the methodology used for primary analysis. Stratification for A-study and B-study will be done as for primary variables. Efficacy variables that are proportions will be analyzed using Mantel-Haenszel test, controlling for Stratum, if appropriate. For the analysis of the categories for responders, a Cochran-Mantel-Haenszel test will be used. Methodologies for variables that are proportions will include construction of confidence intervals for each group and for the difference between groups. For analysis, Fisher's exact test will be used for single-population analysis, and a Mantel-Haenszel test will be used for analyses combining data across strata.

Responders based on the ADAS-cog total score, will be assessed using cumulative percentage plots. Similarly, responders based on the CDR-sb score will be assessed using cumulative percentage plots. The y-axis will show the cumulative percentage of patients who achieved the specific measure of improvement in the ADAS-cog (or CDR-sb) total score shown on the x-axis with a separate cumulative percentage curve for each treatment group.

The proportion of participants who experience loss of one global stage on the CDR will be assessed at each Visit using logistic regression with treatment (as a categorical/class variable), and baseline CDR global score (as a continuous variable). Summary measures from the analysis will include the odds ratio, 95% confidence interval for the odds ratio, and p-value for treatment comparison. Additionally, the proportion of participants in each CDR global stage will be presented.

Kaplan-Meier plots will be provided for each time-to-event variable. For each day, the "survival probability" will be computed by the product-limit method. Time-to-event endpoints may be modelled using Cox proportional hazards models with fixed effects for treatment and baseline measures as a covariate for supportive purposes. The estimated hazard ratio between Azeliragon and placebo will be presented with associated p-values and 95% confidence intervals.

Time to loss of one global stage on the global CDR will include Kaplan-Meier curves. Survival estimates for treatment groups will be compared using the logrank statistic. Observations will be treated as right censored for participants who complete the study without a loss of one stage on the global CDR score or who discontinue the study prematurely.

Subgroup analyses will be done as identified subsequently; data-driven subgroup analyses may be done as exploratory analyses.

For change from Baseline in plasma concentrations of A $\beta$  species, an MMRM analysis similar to that described for the co-primary endpoints with baseline plasma concentrations of A $\beta$  species as a continuous covariate will be performed. Transformation using logarithms may be needed, depending on the distribution.

For change from Baseline in MMSE, an MMRM analysis similar to that described for the co-primary endpoints will be performed, with baseline MMSE as a continuous covariate.

For change from Baseline in NPI, an MMRM analysis similar to that described for the co-primary endpoints will be performed, with baseline NPI as a continuous covariate.

Individual item responses on the RUD questionnaire and the total caregiver time spent assisting the patient based on the RUD questionnaire will be summarized by treatment group.

For change from baseline in DEMQOL-Proxy total score, an ANCOVA analysis with Baseline DEMQOL-Proxy as a continuous covariate will be performed.

If the distribution of any of the above parameters, key secondary, or other secondary endpoints does not appear to be normally distributed, the rank analogues will be utilized.

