7. MRI consistent with a diagnosis of probable Alzheimer's disease. A head CT scan may be used for evaluation if there is a documented contraindication to an MRI (e.g. pacemaker).
8. Mini-Mental State Exam (MMSE) score of 21-26 inclusive at screening.
9. CDR global score of 0.5 or 1 at screening.
10. Rosen-Modified Hachinski Ischemia Score ≤ 4 at screening.
11. Participants must be on a stable dose of a background cholinesterase inhibitor and/or memantine (approved by the relevant health authority where the trial is being conducted) at least 3 months prior to randomization and must agree not to change the dose during the study period unless the investigator judges that the dose needs to be reduced or stopped due to a safety and/or tolerability reason.
12. No clinically significant, (in the opinion of the investigator) laboratory abnormalities at screening. If the results of clinical laboratory testing are outside normal reference ranges, the subject may be enrolled but only if these findings are determined to be not clinically significant by the investigator. This determination must be recorded in the subject's source documents. A summary of values of potential clinical concern is provided in [APPENDIX 1](#).
13. Subject must be able to ingest oral medications.

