6.1 SCREENING

For logistical purposes, up to 60 days will be allowed for screening to confirm that participants meet all selection criteria for the study. It is strongly encouraged that the screening period is minimized to the shortest possible duration whenever possible. The investigator (or an appropriate delegate at the investigator site) will obtain informed consent from each subject, caregiver/informant, and where appropriate, legally authorized representative in accordance with Subject Information and Informed Consent/Assent (where this is in accordance with local laws, regulations and ethics committee policy). The screening assessments may be separated out into more than one visit if required. Refer to the Schedule of Events for a tabular presentation for screening activities.

The following activities will be completed:

- Complete informed consent/assent process (where this is in accordance with local laws, regulations and ethics committee policy) resulting in a signed ICF(s) by the appropriate parties.
- Assign screening identification number.
- Complete MMSE to determine subject eligibility. If subject is eligible based on the MMSE, proceed with the remainder of screening visit in any order.
- ADAS-Cog
- The Columbia Suicide Severity Scale (C-SSRS)
- CDR (calculation of both global score and sum of boxes score global)
- Demographic information (i.e., sex, date of birth, race/ethnicity).
- Complete medical and surgical history, including family medical history of dementia.
- Record and review concomitant medications and any discontinued medication in the 60 days prior to the Screening visit.
- History of drug, alcohol and tobacco use.

- Complete physical and neurological exams.
- Rosen-Modified Hachinski Ischemia Scale
- Height and body weight.
- Vital signs: blood pressure (supine), pulse rate.
- Single 12-lead electrocardiogram (ECG).
- Review of inclusion and exclusion criteria.
- Blood and urine specimens for safety laboratory tests (serum chemistry, hematology, UA) will be collected, in addition to the following:
 - Serum glucose and HbA1c;
 - Hepatitis screens (including hepatitis B surface antigen, hepatitis B core antibody, hepatitis B surface antibody, and hepatitis C antibody);
 - Syphilis test. If positive, a standard confirmation test will be obtained;
 - Thyroid function (T3, T4, and TSH);
 - Vitamin B12 (and MMA if indicated, e.g., if serum B12 level <211 pg/mL);

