6.2 STUDY PERIOD

6.2.1 Baseline (approximately Day -7-Day 1)

- ADAS-cog, MMSE, CDR-sb, ADCS-ADL, COWAT, CFT, Trail Making Test (Versions A and B), NPI, RUD Lite, DEMQOL-proxy
- C-SSRS.
- Review of inclusion and exclusion criteria including the results of the MRI scan.
- Brief physical and neurologic examination.
- Update concomitant medications.
- Weight.
- Assess baseline symptoms/adverse events.
- 12-lead electrocardiogram (ECG) (performed in triplicate).
- Vital signs: blood pressure (supine), pulse rate.
- Baseline FDG-PET (if applicable).
- Collect blood sample for plasma retention and storage.
- Blood sample for ApoE genotyping.
- Blood and urine sampling for safety labs including HbA1c.
- Collect blood samples for PK and PD.
- Randomize subject if eligible.
- Dispense study drug if eligible.
- Subject begins taking study medication in the clinic as soon as baseline procedures are completed (noted as Month 0 [Day 1] on [Table 1](#). Schedule of Activities).

If the baseline assessments are performed on more than one day, up to 7 days are allowed for completion of baseline procedures prior to subject randomization and dosing. The 7 day window will begin on the day that the first baseline assessment is performed and ends on the day when the subject is randomized and study drug is administered.

If it is necessary to extend the 7 day period for any other reason (e.g., schedule conflicts, patient/caregiver/informant illness, inclement weather) the Sponsor should be contacted for approval and the visit window may be extended up to 7 days. In this case, re-review of the inclusion/exclusion criteria and concomitant medications should occur within 7 days prior to the first dose to ensure that the patient continues to be appropriate for the study. Other baseline procedures may be repeated at the discretion of the Investigator, but are not required. The 60 day period from screening to first dose will remain in effect. Should the overall screening time exceed 60 days, re-screening will be required.

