9.0 DATA ANALYSIS/STATISTICAL METHODS

The statistical considerations summarized in the following subsection outline the plan for data analysis of this study. A final and complete Statistical Analysis Plan (SAP) will be finalized prior to unblinding the data from the study. The SAP will supersede the protocol. Any deviations from the planned analyses will be described and justified in the final integrated study report.

This trial describes two studies with a common infrastructure in a single protocol. Statistical analysis of the clinical efficacy variables will be done for each of the studies separately. Statistical analysis of safety and imaging data will be done for the study as a whole (combined).

Continuous variables will be presented showing number of observations available, mean, median, minimum, maximum, 1st and 3rd quartiles, and standard deviations (or standard errors, depending on the variable) by visit. Categorical variables will be presented showing frequencies and percentages by visit.

All tests will be 2-sided and use an overall study-wise $\alpha = 0.05$ unless otherwise stated. SAS Version 9.1 or later will be used. Medical dictionary for Regulatory Activities.

(MedDRA) Version 16.0 or later will be used for coding adverse events. Medications will be coded using WHO Drug Dictionary (WHODD) Version March 2009 or later.

This study is planned using an enrichment strategy, following the draft regulatory guidance depicted in the FDA guidance *Enrichment Strategies for Clinical Trials to Support Approval of Human Drugs and Biological Products* (draft guidance, December, 2012). This study features a conditional sequential approach to hypothesis testing to control alpha, similar to methods using Bauer closed procedures, which are referenced in the FDA adaptive design guidance FDA guidance *Adaptive Design for Clinical Trials for Drugs and Biologics* (draft guidance, February 2010) referenced above), and principles for subgroup analyses.

This study comprises two independent sub-studies in one main study for purposes of independent replication for the co-primary variables: A-Study is composed of the first approximately 400 patients randomized; B-Study is composed of the remaining approximately 400 patients randomized. The study as a whole will be analyzed for specified inferential purposes. A-Study and B-Study will be randomized separately.

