9.5.3 Statistical Methodology for Secondary and Other Efficacy Analysis

Secondary and exploratory endpoints that are measurement variables will use similar statistical methodology to the methodology used for primary analysis. Efficacy variables that are proportions will be analyzed using Mantel-Haenszel test, controlling for Stratum, if appropriate. For the analysis of the categories for responders, a Cochran-Mantel-Haenszel test will be used.

Methodologies for variables that are proportions will include construction of confidence intervals for each treatment group and for the difference between groups. For analysis, Fisher's exact test will be used for single-population analysis, and a Mantel-Haenszel test will be used for analyses combining data across strata.

Methodologies for time-to-event variables will include construction of 95% confidence intervals for each group separately and for the difference between groups. For analysis, a Wilcoxon test will be used for single-population analysis, and a van Elteren test will be used for analyses combining data across strata.

Subgroup analyses will be done as identified in the SAP.

Responders based on the ADAS-cog total score, will be assessed using cumulative percentage plots. Similarly, responders based on the CDR-sb score will be assessed using cumulative percentage plots. The y-axis will show the cumulative percentage of patients who achieved the specific measure of improvement in the ADAS-cog (or CDR-sb) total score shown on the x-axis with a separate cumulative percentage curve for each treatment group.

Time to loss of one global stage on the global CDR will include Kaplan-Meier curves. Survival estimates for treatment groups will be compared using the logrank statistic. Observations will be treated as right censored for participants who complete the study without a loss of one stage on the global CDR score or who discontinue the study prematurely.

The proportion of participants who experience loss of one global stage on the CDR will be assessed at each Visit using logistic regression with treatment (as a categorical/class variable), Baseline CDR global score (as a continuous variable).

Summary measures from the analysis will include the odds ratio, 95% confidence interval for the odds ratio, and p-value for treatment comparison. Additionally, the proportion of participants in each CDR global stage will be presented.

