#### **4.1.5.6 Clinical Dementia Rating Scale (CDR):**

- Global CDR Range:
  - 0 = normal; healthy individuals
  - 0.5 = questionable dementia
  - 1 = mild dementia
  - 2 = moderate dementia
  - 3 = severe dementia.
- CDR sum-of-boxes (CDR-sb) range: CDR-sb scores range from 0 to 18 with higher scores indicating greater cognitive impairment.
- Brief description: The CDR scale is used as a global measure of dementia and is completed by a clinician in the setting of detailed knowledge of the individual patient collected from interviews with the patient and caregiver ([Berg, 1988](#)). The CDR describes 5 degrees of impairment in performance on each of 6 categories including memory, orientation, judgment and problem solving, community affairs, home and hobbies, and personal care. Much of the information will therefore already have been

gathered, either as part of normal clinical practice or as part of a research study. The interview takes approximately 40 minutes to administer.

The scores for each category can also be summed and this is known as the sum of box score (CSR-SB). The CDR will be conducted at Baseline and at Months 3, 6, 12 and 18 or in the event of early termination. To avoid patient fatigue, the CDR should be performed on a separate visit day than the other cognitive tests.

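### The logistic model for CDR stage loss should keep baseline CDR global score and add baseline CDR-sb, which the same CDR already yields

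*SAP*

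**What the plan says.** SAP 5.2.2 analyses the proportion losing a CDR global stage at each visit by "logistic regression with treatment (as a categorical/class variable), and baseline CDR global score (as a continuous variable". Protocol 9.5.3 has the same model: "logistic regression with treatment (as a categorical/class variable), Baseline CDR global score (as a continuous variable". Neither sentence names another covariate.

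Protocol 4.1 requires a "CDR global score of 0.5 or 1 at screening". The CDR is repeated at Baseline, and no limit on the score is stated there.

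One CDR gives both measures. Protocol 6.1 lists "CDR (calculation of both global score and sum of boxes score global", and the Baseline visit (protocol 6.2.1) collects "ADAS-cog, MMSE, CDR-sb, ADCS-ADL, COWAT, CFT, Trail Making Test (Versions A and B), NPI, RUD Lite, DEMQOL-proxy". SAP 4.1.5.6 states that "CDR-sb scores range from 0 to 18 with higher scores indicating greater cognitive impairment".

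Three other places bear on the point:
- SAP 5.2 puts the randomization stratum (screening ADAS-cog, cut at 19) into efficacy analyses as a main effect. The stage-loss sentence does not repeat this.
- SAP 5.2.2 allows a supportive Cox model for time-to-event endpoints and leaves its baseline covariate unspecified.
- Protocol 2.2 lists the stage-loss proportion among the other secondary endpoints. It is not in the ranked list #1 to #8 of SAP 4.1.3, and SAP 4.1.4 lists only the time to stage loss.

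**The concern.** Whether a patient reaches the next stage within 18 months depends on how near that stage the patient starts. With entry at 0.5 or 1, the global score says which threshold applies but not how far away it is. CDR-sb carries that distance and costs nothing to use.

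Elsewhere the plan adjusts for the fine-grained baseline of the scale under analysis: the primary MMRM for CDR-sb, and the models for MMSE, NPI and DEMQOL-Proxy. Here it uses a near-binary baseline although a finer one from the same instrument is available.

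At stake is some precision in a reported odds ratio, confidence interval and p-value, and correction for chance imbalance in severity within a stage.

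**Working it through.** **The plan's own CDR-sb figure.** The inputs are a difference of 0.9, an SD of 2.4, 90% power and two-sided alpha 0.05 (protocol 9.1; on sidedness, protocol 9.0: "All tests will be 2-sided and use an overall study-wise"). The normal approximation gives n per group = 2 × (1.960 + 1.282)² × 2.4² / 0.9² ≈ 149.5, so 150. The exact t-test search gives 151. The plan states 152, where power is 90.3%, and 304 / 0.8 = 380 randomized. The figure reproduces. The plan states no power, event rate or odds ratio for stage loss.

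**Sample size for this endpoint.** Inference on secondary variables uses A-study and B-study combined (SAP 5.2), so n = 800 × (1 − 0.20) = 640.

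**Why severity within a stage matters, and why the stage must stay.** Assume stage cut-points of 4.25 and 9.25 on CDR-sb, a mean placebo decline of 1.5, and normal change with the plan's SD of 2.4. The chance of stage loss is 1 − Φ((cut-point − baseline − 1.5) / 2.4):
- Stage 0.5, CDR-sb 1.5: 1 − Φ(1.25 / 2.4) = 1 − Φ(0.52) ≈ 30%
- Stage 0.5, CDR-sb 4.0: 1 − Φ(−1.25 / 2.4) = 1 − Φ(−0.52) ≈ 70%
- Stage 1, CDR-sb 4.5: 1 − Φ(3.25 / 2.4) = 1 − Φ(1.35) ≈ 9%
- Stage 1, CDR-sb 7.0: 1 − Φ(0.75 / 2.4) = 1 − Φ(0.31) ≈ 38%

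Risk rises within each stage, which the planned model cannot see. It drops sharply between 4.0 and 4.5, where the stage changes, which one linear CDR-sb term without the stage cannot see.

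**Simulated power, cut-point model.** n = 640, difference 0.9, SD 2.4, two-sided 0.049, 1,500 trials per row. Assumed baseline CDR-sb is 1.5–4 at stage 0.5 and 4.5–7 at stage 1.

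| Share at stage 1 | Placebo decline | Stage loss, placebo / azeliragon | Global only (plan) | CDR-sb only | Both | Gain from adding |
|---|---|---|---|---|---|---|
| 30% | 1.5 | 41.5% / 29.1% | 93.7% | 92.1% | 94.6% | +0.9 |
| 30% | 2.5 | 56.1% / 42.8% | 93.3% | 92.0% | 94.6% | +1.3 |
| 50% | 1.5 | 35.8% / 24.5% | 90.7% | 88.2% | 92.3% | +1.6 |
| 50% | 2.5 | 50.0% / 37.3% | 92.4% | 90.5% | 94.9% | +2.5 |

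With a difference of 0.5, adding CDR-sb gained 2.9 to 3.6 points. In all eight pooled scenarios the swap lost power, by 0.8 to 2.8 points.

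**Other baseline shapes.** With a gamma baseline (mean 4.2, clipped to 0.5–9), cut-points 4.5 and 9.5, decline 1.8, difference 0.9 and two-sided 0.05:
- Stage loss was about 41% versus 29%. Power was 89.9% as planned, 87.6% with the swap and 93.3% with both.
- With half-point scores the three figures were 90.8%, 89.9% and 92.7%.
- With staging noise of SD 0.7, adding CDR-sb moved power from 88.3% to 91.7%.
- Where change was allowed to depend on baseline (total SD held at 2.4), the gain was +1.3 points at slope −0.3, +0.7 at −0.6 and +4.6 at +0.2.
- With no treatment effect, the model with both covariates rejected in 4.8% to 5.3% of trials.

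**A model without cut-points.** Here the log-odds of stage loss were set directly (odds ratio 0.65, slope 0 to 0.8 per CDR-sb point, n = 640). This does not use the plan's SD or difference. Adding CDR-sb changed power by −0.3 to +7.0 points: no more than 0.8 points for slopes up to 0.2, and the largest gain (48.1% to 55.1%) at slope 0.8.

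Monte Carlo error for one power value at 1,500 trials is at most √(0.5 × 0.5 / 1,500) ≈ 1.3 points, and smaller for differences between models fitted to the same data.

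**The case against.** Little depends on this model. The endpoint is outside the co-primaries, the key secondary and the ranked list. Time to stage loss is compared by logrank, and the Cox model is optional. The more sensitive form of the outcome, change in CDR-sb, is co-primary and already adjusts for its own baseline. All of this stands, and it keeps the point minor.

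The gain is partly built in: a simulation that defines stage by cut-points on CDR-sb guarantees that CDR-sb is prognostic. This also stands. The documents contain no prognostic estimate, and where CDR-sb had no prognostic value the gain was nil. Noisy staging and baseline-dependent change alter the size but leave a gain in the cases run.

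A reader might infer three stronger things, which the documents do not support:
- *That CDR-sb should replace the global score.* Stage loss is counted from the baseline stage, so the stage belongs in the model. The swap helped appreciably only where the odds of stage loss rose smoothly across both stages (48.1% to 54.5% at best), which sits badly with an outcome defined from the starting stage.
- *That global score is the only severity adjustment.* SAP 5.2 already brings in the randomization stratum, a screening ADAS-cog measure. SAP 5.2.2 also calls for stratification by A-study and B-study.
- *That a larger gain within one sub-study is relevant.* Only the co-primaries are tested by sub-study. Separate summaries of other efficacy variables are descriptive.

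Entering the global score as class rather than continuous changes nothing while it takes two values. It would matter only if a patient's Baseline score fell outside the screening range.

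**Conclusion.** The point holds as a free improvement. The planned model leaves out a baseline measure that is already in the database and that describes severity within a stage. Keeping the global score and adding CDR-sb gains roughly 0 to 5 power points in the pooled analysis of about 640 patients, for example from about 90% to 93%. That range rests on the plan's SD of 2.4 and difference of 0.9, and on assumed cut-points, decline and baseline distribution. The +7.0 extreme needs a steep assumed slope and does not use the plan's inputs.

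The planned analysis is valid as written. It would be wrong to read this as a flaw in a confirmatory test or as a case for dropping the global score.

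**What to change.** In SAP 5.2.2, specify the stage-loss logistic model with treatment, baseline CDR global score, baseline CDR-sb as a continuous covariate, and the randomization stratum that SAP 5.2 requires for efficacy analyses. If the supportive Cox model for time to stage loss is fitted, name the same covariates there. Align protocol 9.5.3 for consistency; protocol 9.0 already lets the SAP supersede it.

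The change must be fixed before unblinding. Protocol 11.1 has each sub-study locked and unblinded as it completes, so it should precede the first of the two.

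The cost is an SAP amendment of a sentence or two, with no new data. The odds ratio becomes conditional on CDR-sb as well as on global stage, and the SAP should say so.

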6.2.9 Month 18 (\pm 7 days)

- ADAS-cog, MMSE, CDR, ADCS-ADL, COWAT, CFT, Trail making test (Versions A and B), NPI, RUD Lite and DEMQOL- proxy.
- C-SSRS.
- Review and record new concomitant medications.
- Assess symptoms/adverse events and by asking the participants to respond to a non-leading question such as “How have you been feeling?”
- Brief physical and neurologic examination.
- Body weight.
- ECG.
- Vital signs: blood pressure (supine) and pulse rate.
- MRI if one was obtained during the screening period. If a CT scan was used for assessing eligibility, then the 18 month MRI scan will not be performed, and the CT scan will not be repeated.
- FDG-PET (if applicable).
- Collect blood sample for plasma retention and storage.
- Blood and urine sampling for safety laboratory testing including HbA1c.
- Collect blood samples for PK and PD.
- Drug accountability. Any discrepancies are recorded in the source and the subject and caregiver/informant are counseled regarding proper dosing compliance.

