##### 4.1.5.1 Alzheimer's Disease Assessment Scale - Cognitive Subscale 70 point (ADAS-cog):

- Range: The scale range is 0 to 70 with higher scores indicating greater cognitive impairment.
- Brief description: The ADAS-cog is a structured scale (approximately 40 minutes to complete) that evaluates memory, orientation, attention, reasoning, language and constructional praxis (Rosen, 1984). The ADAS-cog scoring range for the version used in this study is from 0 to 70. The ADAS-cog will be conducted at Baseline and at Months 3, 6, 9, 12, 15 and 18 or in the event of early termination. The ADAS-cog should always be administered prior to other cognitive measures.

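### Day-by-day Kaplan-Meier curves for events seen only at visits can misstate the Month 18 event probability; the SAP should place events and censoring at nominal visits

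*SAP*

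**What the plan says.** SAP 5.2.2 covers all survival-type variables: "Kaplan-Meier plots will be provided for each time-to-event variable. For each day, the" survival probability "will be computed by the product-limit method". For loss of one CDR global stage it adds a log-rank comparison and this censoring rule: "Observations will be treated as right censored for participants who complete the study without a loss of one stage on the global CDR score". Early discontinuers are censored too. No censoring day is given for either group.

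SAP 5.2.1.1 adds a second family of variables: "Survival techniques will be applied to data assessing time to increase in ADAS-cog of 7 points", repeated for every cut-point from 1 to 20 points.

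The assessments are sparse. For CDR, SAP 4.1.5.6 says "The CDR will be conducted at Baseline and at Months 3, 6, 12 and 18 or in the event of early termination". For ADAS-cog, SAP 4.1.5.1 says "The ADAS-cog will be conducted at Baseline and at Months 3, 6, 9, 12, 15 and 18", or at early termination. Protocol Table 1 and Section 6.2.9 put Month 18 at day 540 with a window of ±7 days.

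The SAP does not say whether an event is dated to the actual or the nominal day, or at which day a curve is read as Month 18. SAP 6.4 covers only how out-of-window assessments are displayed.

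**The concern.** The product-limit method works when patients counted as event-free on a given day are still under observation that day. Here every patient is assessed once in each window. At Months 3 to 15 this does little harm, because a patient seen without the event stays at risk until the next visit. At Month 18 there is no next on-treatment visit. If actual days are used, a completer seen event-free on day 534 has left the risk set before an event found on day 545, although both patients were assessed at the same visit. Later events are divided by an ever smaller number and the end of the curve falls too far.

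At stake is the absolute probability a reader takes from the right-hand end of the curve. For CDR it would sit beside the by-visit proportion with stage loss, also planned in SAP 5.2.2, and could visibly disagree with it.

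**Working it through.** The documents state no Kaplan-Meier probability, event rate or event count, so there is no plan figure to reproduce.

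**Inputs from the documents.** Month 18 window: days 533 to 547, i.e. 15 days (Protocol Table 1). CDR visits at Months 3, 6, 12 and 18; ADAS-cog every 3 months (SAP 4.1.5). About 400 per group with both studies combined (SAP 1.5). Dropout 20% (SAP 1.6).

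**Assumptions.** Actual visit days are used; event-free completers are censored on their Month 18 visit day; true event rates are varied.

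**Closed form.** Let S be the proportion event-free before Month 18, and p the share of those first found with the event at Month 18. Spread visits evenly over the 15 days. When m fifteenths of the patients are still to be seen, one fifteenth attends and a share p of them has the event, so that day's factor is 1 − p/m.

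- Truth: 1 − S(1 − p)
- Curve at its end (day 547): 1 − S × product of (1 − p/m) for m = 1 to 15
- Curve at day 540: 1 − S × product of (1 − p/m) for m = 8 to 15

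For S = 0.75 and p = 0.15:

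- Truth: 1 − 0.75 × 0.85 = 0.3625
- Day 547: the product is 0.5963, so 1 − 0.75 × 0.5963 = 0.5528, an error of **+19.0 points**
- Day 540: the product is 0.8962, so 1 − 0.75 × 0.8962 = 0.3278, an error of **−3.5 points**

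| p (S = 0.75) | Error at day 547 | Error at day 540 |
|---|---|---|
| 0.05 | +7.8 | −1.1 |
| 0.10 | +14.1 | −2.2 |
| 0.15 | +19.0 | −3.5 |
| 0.20 | +22.7 | −4.8 |
| 0.25 | +25.3 | −6.2 |

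**Simulation, CDR schedule.** 400 per group, 20% dropout, constant hazard, 150 runs per setting. Errors are in percentage points.

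| True 18-month rate | End of curve, even visit days | End of curve, visit days with SD 3 | Day 540, even visit days | Nominal days |
|---|---|---|---|---|
| 10% | +7.2 | +8.9 | −0.8 | −0.4 |
| 20% | +12.4 | +18.5 | −1.5 | 0.0 |
| 30% | +17.2 | +21.6 | −2.3 | +0.1 |
| 40% | +19.0 | +24.5 | −2.5 | −0.2 |
| 50% | +20.5 | +25.9 | −3.3 | +0.3 |
| 60% | +18.9 | +24.2 | −3.9 | +0.3 |
| 70% | +17.2 | +20.2 | −4.4 | 0.0 |

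**Simulation, ADAS-cog schedule.** Over the same range of rates, the error at the end of the curve is +4.4 to +12.0 points with even visit days and +3.5 to +17.0 with SD 3 days. At day 540 it is at most −1.4. A model of the 7-point crossing (SD of change 9 from SAP 1.6; assumed mean decline 3 to 9 points; assumed measurement SD 3 to 5) gives +9.0 to +10.6 at the end and −1.5 to −2.0 at day 540. The last interval is 3 months rather than 6, so fewer first events fall at Month 18.

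**Log-rank test.** In 1500 two-arm runs per setting, actual against nominal days: type I error 5.5% against 5.9%; power at a hazard ratio of 0.8, 42% against 44%; correlation of the test statistics 0.98.

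**The case against.** The strongest reply is that this is one reading of a silent text. A daily product-limit calculation also fits nominal days. The censoring rule speaks of completing the study, and completers who do not enter the extension have a Month 21 follow-up visit. If a share q of the event-free completers is censored after day 547, they stay in the risk set through the window. On the k-th day of the window the factor becomes 1 − p/[(16 − k) + q(1 − p)(k − 1)]. For S = 0.75 and p = 0.15 the error at day 547 is:

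| q | 0 | 10% | 25% | 50% | 100% |
|---|---|---|---|---|---|
| Error (points) | +19.0 | +11.6 | +7.1 | +3.5 | 0 |

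This stands as a limit on the size. It does not remove the point. SAP 6.5 treats follow-up data as unsuitable for analysis and gives extension patients no follow-up visit, so for many completers Month 18 is the natural censoring day. A rule that permits both a 19-point error and none needs settling.

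It is also fair that no Month 18 Kaplan-Meier estimate is called for in the SAP. For these variables it plans plots, log-rank (and, for ADAS-cog, Wilcoxon) tests and hazard ratios, with the Cox model optional. The by-visit logistic regression gives the Month 18 proportion untouched by day-level timing. Time to CDR stage loss is an other-efficacy variable outside the SAP 4.1.3 hierarchy, and the ADAS-cog survival tests are labelled descriptive. All of this stands, and it sets the severity.

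**Conclusion.** The point holds in a limited form. If actual days are used and completers are censored on their Month 18 visit day, the end of the CDR curve overstates the event probability by roughly 7 to 26 points for assumed true rates of 10 to 70%, and the ADAS-cog curve by about 4 to 17. At day 540 the sign reverses: 0 to 4.4 points too low for CDR in the simulation, up to 2.0 for ADAS-cog. Later censoring of some completers reduces the overstatement.

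The documents do not support three stronger readings that a reader might infer:

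- **That the Month 18 probability is overstated by a fixed 15 to 25 points.** That size needs CDR stage loss, both dating assumptions, a curve read at its end, and a true rate of about 30 to 70% (about 20 to 70% if visits cluster near day 540). No rate is given.
- **That the treatment comparison is invalid.** Visit timing is the same in both arms, and the log-rank test hardly changes.
- **That the hazard ratio is wrong.** No error in it has been shown.

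Severity is low. The point concerns the displayed curves of supportive and exploratory variables. No co-primary, key secondary or hierarchically tested endpoint is affected.

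**What to change.** In SAP 5.2.2 and 5.2.1.1, replace the daily rule with one sentence. Events and censoring are assigned to the nominal scheduled visit (Months 3, 6, 12 and 18 for CDR; 3, 6, 9, 12, 15 and 18 for ADAS-cog), and event-free patients are censored after the events at that visit. Compute the Kaplan-Meier curve and the log-rank test on those times. In the simulations this brought the error within 0.4 points in every setting, for both schedules. Efficacy data from early termination visits can keep the nearest-visit mapping already in SAP 6.5.

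The cost is a change of SAP wording and minor programming. The curve becomes a step function with four steps (CDR) or six (ADAS-cog). A discrete-time or interval-censored model for the hazard ratio is an option, not a requirement.
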